3.2.2 Exploratory Efficacy Outcomes

- 3.2.2.1** PTSD score as measured by the PTSD Checklist for DSM-5 (PCL-5)
- 3.2.2.2** Depression score as measured by the Patient Health Questionnaire (PHQ-9)
- 3.2.2.3** Physical and Mental Health Summary scores as measured by the Veterans Rand 12-Item Health Survey (VR-12)
- 3.2.2.4** Change in phosphatidyl ethanol (Peth) from baseline to weeks 8 and 12

3.2.3 Safety Outcomes

Rates, severity and relatedness of adverse events including serious adverse events, study drug-related adverse events, and deaths will be evaluated. See section 8 of the protocol for specific details on safety parameters (i.e. definitions of AEs) and classifications (i.e. severity, relationship, and expectedness definitions).

[figure not shown]
4 STUDY METHODS

4.1 Overall Study Design and Plan

This randomized, double-blind, placebo-controlled, multi-site study evaluates the efficacy of SL-BUP combined with XR-NTX in the treatment of comorbid AUD and PTSD. Recruitment is based on convenience sampling of treatment-seeking veterans and active duty service members. Following screening and baseline visits, eligible patients are randomization to receive one of two treatments in a double-blind fashion for 12 weeks:

- Treatment A (SL-BUP 2mg and XR-NTX 380mg) or**
- Treatment B (SL-PLC and XR-PLC).**

The treatment allocation ratio for the treatment vs. placebo (PLC) regimens is **1:1** and is stratified by site, presence of concomitant antidepressants, and gender using a random permuted block scheme with variable block size (see below Figure). The study population will consist of ~ 90 Veterans with combat-related PTSD and co-morbid AUD. Detailed eligibility criteria for participant inclusion in this study are included in Section 4.2, below.

Study Design: RCT of KOR Antagonist in the treatment of Comorbid AUD and PTSD

4.2 Study Population

4.2.1 Subject Characteristics

The study population is defined by the following eligibility criteria:
Inclusion Criteria

To be enrolled in this study, participants must meet the following criteria.

1. Male or female, 18 to 65 years of age, capable of reading and understanding English, and able to provide written informed consent (i.e. no surrogate).
2. Current moderate to severe AUD as determined by MINI International Neuropsychiatric Interview for DSM-5 (MINI-5).
3. At least two recent episodes of heavy drinking (>5 standard drinks/sessions for men and >4 standard drinks/sessions for women) over the past 30 days, and heavy drinking pattern defined as 14 drinks per week for women and 21 drinks per week for men for at least 2 of a 4-week interval within the 90 days prior to baseline; i.e. at least Moderate Risk level on WHO category.
4. PTSD diagnosis defined by MINI-5 at screening; symptoms must be present according to the DSM-5 criteria, i.e. minimum number in each cluster: at least 1 B symptom, 1 C symptoms, 2 D symptoms and 2 E symptoms.
5. Clinician Administered PTSD Scale for DSM-5 (CAPS-5) total score ≥ 26 for the past one week at baseline.
6. Females of child-bearing potential must be using medically acceptable birth control (e.g. oral, implantable, injectable, or transdermal contraceptives; intrauterine device; double-barrier method) AND not be pregnant OR have plans for pregnancy or breastfeeding during the study.

7. Must have a CIWA-Ar score of < 8 prior to randomization.
8. Willing and able to refrain from medications thought to influence alcohol consumption (other formulations of naltrexone, disulfiram, acamprosate, topiramate, ondansatrin, baclofen, and gabapentin).
9. Willing and able to refrain from psychotropic medications: stimulants/ADHD treatment, Alzheimer's medications, antipsychotics, benzodiazepines, antianxiety medications, mood stabilizers, and other sedatives.

Exclusion Criteria:

To be enrolled in this study, participants *must not meet* the following criteria.

1. Current diagnosis of DSM-5 bipolar I, schizophrenia, schizoaffective, and/or major depressive disorder with psychotic features (defined by MINI-5 at screening).
2. Increased risk of suicide that necessitates inpatient treatment or warrants therapy excluded by the protocol, and/or current suicidal plan, per investigator clinical judgement, based on interview and defined on the Columbia Suicidality Severity Rating Scale (C-SSRS).
3. Treatment with trauma-focused therapy for PTSD (e.g. Cognitive Processing Therapy, Prolonged Exposure, or EMDR) within two weeks of baseline study visit. Note: Supportive psychotherapy in process for PTSD at time of Screening may be continued.
4. Current diagnosis of moderate or severe non-alcohol substance use disorder (except for caffeine and nicotine) during the preceding 1 month, based on participant screening interview. Participants must agree to abstain from illicit drugs during the study. Patients who utilize cannabis but do not meet substance use disorder criteria are permitted.
5. Use of opioids within 2 weeks of baseline or opioid use disorder in the previous 90 days.
6. History of severe traumatic brain injury (TBI) per Ohio State University TBI Identification Method. Note: history of mild or moderate TBI is allowed.
7. Any clinically significant, uncontrolled, or medical/surgical condition that would contraindicate use of SL-BUP + XR-NTX, or limit ability to complete study assessments, including seizures (other than childhood febrile seizures), severe renal insufficiency, significant arrhythmia or heart block, heart failure, or myocardial infarction within the past 2 years, severe thrombocytopenia or hemophilia, severe hepatic failure, complete hearing loss, and/or need for surgery that might interfere with ability to participate.
8. Clinically significant laboratory abnormalities, including a thyroid stimulating hormone (TSH) >1.5 times upper limit of normal, hyperthyroidism, and aspartate aminotransferase and/or alanine aminotransferase > 3 times upper limit of normal; cardiovascular findings QTcF >500 msec on electrocardiogram (ECG) or blood pressure >190/110.
9. History of allergic reaction, bronchospasm or hypersensitivity to a naltrexone or buprenorphine.
10. Unable or unwilling to refrain from medications thought to influence alcohol consumption (see inclusion criteria above.)
11. Unable or unwilling to refrain from psychotropic medications (see inclusion criteria above); with the exception of stable doses of antidepressants, prazosin, and non-

benzodiazepine hypnotics and non-benzodiazepine anxiolytics to treat PTSD or insomnia.

12. Persons who are imprisoned, of minor age, diagnosed with dementia, diagnosed with a terminal illness, or otherwise require a surrogate to provide informed consent.

4.3 Study Arm Assignment and Randomization

At baseline, participants who meet eligibility criteria are randomized to treatment A (buprenorphine 2mg SL with naltrexone 380mg IM) or treatment B (SL placebo and IM placebo). The treatment allocation ratio for the treatment vs. placebo regimens is 1:1 and is stratified by site, presence of concomitant antidepressants, and gender using a random permuted block scheme with variable block size. The randomization schedule is created by the PASA statistician who coordinates with the local research pharmacies and develops the web-based randomization assignment system. At week 8, the participants will remain on the assigned treatment and dose from week 8 to 12.

4.4 Masking and Data Lock

4.4.1 General Masking Procedures

This is a double-blind study so participants and study staff are masked to treatment assignment. Any unmasking will be reported as a protocol deviation. In the event of an emergency, study investigators may unmask without advance permissions but must promptly report the unmasking within 24 hours by contacting PASA leadership.

4.4.2 Database Lock

The database will be locked after the completion of all study follow-up visits for all participants. Once all participants have completed all follow-up visits, a final query report will be generated and the study coordinators will address data queries within Medidata Rave. The database will be locked after all final queries have been resolved (estimated ~2 weeks after all follow-up visits completed). Randomization assignment will not be unmasked beyond the details of Section 4.4.1 until after database lock is finalized.

4.5 Study Flow Chart of Assessments and Evaluations

Assessments	Schedule of Assessments: Screening, Baseline, Week (#) or Telephone (T) Visit																
	Screen	Baseline	Baseline (Day 2)	Week 1	Week 2	T	Week 4	T	Week 6	T	Week 8	Week 8 (Day 2)	T	Week 10	T	Week 12	T
PAYMENTS	25		75	30	60		30		30		80		30		40		20
Assessments to Qualify for Study and Characterize Population																	
Demographics	X																
Smoking Status	X										X					X	
MINI	X																
H&P	X																
VS, BMI, BrAC	X	X		X	X		X		X		X			X		X	X
Labs/ECG	X															X	
Pregnancy	X						X				X					X	
CIWA-Ar	X	X														X	X
COWS	X															X	X
ADS	X																
OSU-TBI	X																
BIS	X																
Psychophysiology Study																	
Fear Conditioning			X								X						
Psychophysiological Stress Reactivity			X	X		X					X	X					
Alcohol Related Outcomes																	
TLFB	X	X		X	X		X		X		X			X		X	
OCDS		X		X	X		X		X		X			X		X	
Peth		X									X					X	
Serum BUP											X					X	
SIP		X									X					X	
DAQ		X			X						X						
Urine Drug Screen	X	X		X	X		X		X		X			X		X	
PTSD Related Outcomes																	
LEC-5 Checklist		X															
PCL-5		X	X		X	X		X		X		X		X		X	
CAPS-5		X					X				X					X	
Psychological Symptoms and Quality of Life																	
C-SSRS			X								X						
PHQ-9		X					X				X					X	
VR-12		X									X					X	
CGI-S		X		X	X		X		X		X			X		X	
CGI-I				X	X		X		X		X			X		X	
Adverse Events and Concomitant Medications																	
Con-Meds	X	X		X	X		X		X		X			X		X	X
Adverse Events				X	X	X	X	X	X	X	X	X		X	X	X	X
Study Drug***																	
Dispense Drug				X	X	X		X		X		X		X			
Pill Counts				X	X		X		X		X			X		X	
Study Drug Knowledge																X	

5 ANALYSIS POPULATIONS

5.1 Intention-to-Treat

The primary and exploratory analyses will be based on the intention-to-treat (ITT) principle, with data from all participants analyzed according to the arm to which they were randomized irrespective of the amount intervention received. This includes participants initially randomized to the high-dose treatment arm (SL-BUP 8mg and XR-NTX 380mg) that was removed from the protocol (Version 5). Participants who receive intervention but do not complete the study will be used in all analyses for which data are available. This approach ignores noncompliance, protocol deviations, withdrawal and lost-to-follow-ups. Analysis of the ITT population avoids overoptimistic estimates of the efficacy of an intervention resulting from the removal of non-compliers, accepting that protocol deviations occur in actual clinical practice (Heritier, Gebski, & Keech, 2003).

5.2 Per-Protocol

As in most clinical trials, some participants may not adhere to the intervention they were randomized to receive, reducing fidelity to the intervention as designed and potentially changing the effectiveness of the intervention. The most likely form of noncompliance will be lack of adherence to the randomized medication. The potential impact of this noncompliance is underestimating the magnitude of the true treatment effect. To assess this, in addition to the ITT analyses, we will also conduct all analyses at the primary time point (8-weeks) using a per protocol population; defined as completion of the NTX/Placebo injections at baseline and week 4, as well as completion of 80% of Buprenorphine pills dispensed from baseline through week 8. The per-protocol analysis provides an estimate of the true efficacy of an intervention (i.e., among those who completed the treatment as planned) (Ranganathan, Pramesh, & Aggarwal, 2016). No other analysis populations are defined for this protocol.

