6.1.5 DOSING AND ADMINISTRATION

The dose of XR-NTX is 380 mg delivered intramuscularly [gluteal; alternating buttocks for each subsequent injection and documentation of injection site and date in the Computerized Patient Record System (CPRS) source notes] every 4 weeks or once a month by research MD, APN or RN. XR-NTX and XR-PLC must be suspended **only** in the diluent supplied in the dose kit and must be administered with the needle supplied in the dose kit. All components (i.e., the microspheres, diluent, preparation needle, and an administration needle with safety device) are required for administration. A spare administration needle is provided in case of clogging. Do not substitute any other components for the components of the dose kit.

SL-BUP or SL-PLC will be ordered by an investigator/co-investigator with prescribing privileges in the quantity of pills (one per day) needed for the exact number of days until the next scheduled visit (may vary according to patient needs and location, (i.e., can dispense a four-week supply with number of tablets needed until next scheduled visit for the injection). The local pharmacy or research pharmacist dispenses the medication. The medication management provider and/or the research coordinator reviews the medication instructions with the participant. The participant is informed that he/she must bring any unused portion of the study medication to subsequent visits so that the prescriber can issue the correct number of pills to allow for enough supply to last until the next scheduled visit. Also, the participant is informed that if she/he misses a dose, she/he should take the next dose as soon as possible.

If for any reason there is SL-BUP or SL-PLC study medication that will go unused, the participant will place the unused medication in a Take-Away Medication Recovery System tamper-resistant envelope and place in a US postal service mailbox to be sent to a pharmacy destruction service. This can vary by site and may be done at each visit and/or at the end of the study.

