*Smoking: Will include both tobacco and marijuana at baseline, and marijuana only at Weeks 8 and 12. **H&P, laboratory tests, and ECG within previous 90 days is acceptable at screening visit. (At Week 12: The H&P, thyroid test, and ECG do not need to be repeated.) If baseline level was between 3x-5x ULN, ALT and AST needs to be repeated at week 4 and week 8 visit. At Week 8, GGT needs to be repeated. ^aVital signs and breathalyzer on Week 2, 6, 10 may be omitted due to COVID-19 reduction of in-person visits. ^bPsychophysiological assessments are optional so as to not be a barrier to enrollment or randomization. ***Day of Randomization is on Baseline. The schedule of follow-up visits is anchored to Baseline. ****CAPS-5 and C-SSRS can be administered prior to day of baseline so long as it is within one week of day of randomization and scores are entered as baseline. ****C-SSRS can be done either at screening or baseline visit, as well as Week 8. ^{\$}Baseline and week 8 drug dispensing will occur on day 1 if not participating in psychophysiology testing and on day 2 if participating in testing

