7.3.3 BASELINE AND RANDOMIZATION VISITS

The investigators and CRCs provide ongoing support and education during the study to reinforce the participants' commitment and resolve logistical barriers to keeping the appointments. Participant burden is kept to a minimum (i.e., small number of assessments and low frequency). Adherence and attendance are vital to the success of both treatment and the study. Patient education on study procedures and the treatment approach in the study is the cornerstone to promote adherence. To maximize participant retention, study coordinators are trained to have a substantial focus, especially in the first several meetings with participants, on developing a strong alliance, educating them about the study, understanding the importance of adhering to treatment, what is expected of them as a study participant, and eliciting commitment.

At the baseline visit, the research team evaluates the participant per the study instruments listed in the Schedule of Assessments table in 7.3.1. Participants undergoing the optional two-day psychophysiological assessments, as described above, will complete both days of the psychophysiological testing prior to beginning the study medication.

The research medication provider enters the medication orders (one for XR-NTX and one for SL-BUP) and the local site pharmacy dispenses the study medication according to the randomized assignment to one of two treatments:

- **Treatment A (SL-BUP 2mg + XR-NTX 380mg) or**
- **Treatment B (SL-PLC and XR-PLC).**

SL-BUP is taken daily and XR-NTX is given every 4 weeks. All medications are dispensed by local site pharmacies with clearly labeled instructions.

The participant receives the first dose of XR-NTX injectable in the research clinic and remains in the clinic under the supervision of the research team for approximately 1 hour after the 1st dose is administered.

The medication provider or trained CRC reviews the medication instructions with the participant (how to administer sublingual, keeping up with medication dosing, and need to return any

unused medication to the research medication provider at the next visit). The participant initiates SL-BUP on the following day.

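### The per-protocol tablet rule in SAP 5.2 counts against pills dispensed, so under net resupply early missed tablets leave the denominator

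*SAP*

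**What the plan says.** SAP 5.2 repeats the Week 8 analyses in a per-protocol set. Entry requires the Baseline and Week 4 injections and "completion of 80% of Buprenorphine pills dispensed from baseline through week 8". The section gives the purpose of the set as estimating efficacy "among those who completed the treatment as planned".

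The supply rules are in Protocol 6.1.5. Tablets are ordered "in the quantity of pills (one per day) needed for the exact number of days until the next scheduled visit", and sites "can dispense a four-week supply with number of tablets needed until next scheduled visit for the injection". Participants bring unused tablets back "so that the prescriber can issue the correct number of pills to allow for enough supply to last until the next scheduled visit". The same section provides for leftover tablets to be sent for destruction and adds: "This can vary by site and may be done at each visit and/or at the end of the study".

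The Protocol 7.3.1 schedule marks dispensing at Baseline, Week 4 and Week 8, and its footnote confirms the last of these: "Baseline and week 8 drug dispensing will occur on day 1 if not participating in psychophysiology testing". On the start of dosing, Protocol 7.3.3 says: "The participant initiates SL-BUP on the following day".

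Missed and taken tablets are recorded separately (SAP 9.2, pill count; SAP 9.6.2), but SAP 5.2 does not refer to those counts.

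**The concern.** A rule meant to identify treatment completed as planned should have the planned number of doses as its denominator. Pills dispensed equals that number only if every participant is issued the full supply whatever is left over. If returned tablets are offset against the next issue, a tablet missed before Week 4 reduces what is issued at Week 4 and so disappears from the denominator. A tablet missed after Week 4 stays in it.

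Two consequences follow. Participants with the same total intake can be classified differently because of when they missed doses. Some participants well below 80% of planned doses can also count as treated as planned. SAP 5.2 names poor adherence to medication as the most likely form of noncompliance and as the reason for running this analysis, so the adherence rule matters to its purpose.

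**Working it through.** The 80% is a chosen cut-off, so there is no derivation to reproduce. The check is tablet accounting.

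**Inputs and assumptions**
- One tablet daily (Protocol 6.1.5), first tablet the day after the first injection (7.3.3), Week 8 visit on day 56: 56 planned tablets.
- Issues that count: Baseline and Week 4 (7.3.1), 28 days apart.
- Net resupply (an inference from 6.1.5): all leftovers are returned and carried forward, so the Week 4 issue = 28 − leftovers.
- Visits on their nominal dates; the Week 8 issue is not counted.

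**Three participants, each taking 42 of 56 tablets (75% of planned), net resupply**

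| Pattern | Taken by Week 4 | Week 4 issue | Total dispensed | Taken / dispensed | Result |
|---|---|---|---|---|---|
| 14-day gap in Weeks 2-3 | 14 | 28 − 14 = 14 | 42 | 42/42 = 100% | passes |
| 14-day gap in Weeks 6-7 | 28 | 28 − 0 = 28 | 56 | 42/56 = 75% | fails |
| Daily in the first week, then five a week | 7 + 15 = 22 | 28 − 6 = 22 | 50 | 42/50 = 84% | passes |

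**Steady intake at proportion p of planned, net resupply**
- Taken = 56p. Dispensed = 28 + 28 − 28(1 − p) = 28 + 28p.
- Ratio = 56p / (28 + 28p) = 2p / (1 + p).
- 2p / (1 + p) ≥ 0.8 gives 1.2p ≥ 0.8, so p ≥ 66.7%.
- In whole tablets: 19 + 19 = 38 taken and 28 + 19 = 47 dispensed. 38/47 = 80.9% passes, although 38/56 = 67.9% of planned.
- Intake at half the planned rate gives 28/42 = 66.7% and is correctly excluded.

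**Full reissue (leftovers destroyed)**
- Dispensed = 56 whatever is missed, so the ratio equals taken/56.
- The pass mark is 0.8 × 56 = 44.8, so 45 tablets. There is no distortion.

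**Same intake at two sites**
- Steady 70% under net resupply: 1.4/1.7 = 82.4%, passes.
- Steady 70% under full reissue: 70%, fails.

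**The case against.** The strongest objection is that the documents do not fix the supply practice. Protocol 6.1.5 allows leftovers to be destroyed, possibly at each visit, and Protocol 6.2 leaves accounting and destruction to each site pharmacy. If every site destroys leftovers and reissues in full, the rule works as intended. This stands, and it is why the point is conditional. It does not make the present wording safe: if practice differs between sites, equal intake is classified by site rather than by adherence.

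A second objection is that the dosing log holds missed and taken tablets, so the analyst might compute taken / (taken + missed), which restores the planned-dose denominator. That would be sound, but it is not what SAP 5.2 says. It is close to the change proposed here.

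A third is that Protocol 7.3.4 permits doses to be held or taken less often for side effects, so a 14-day gap may be allowed and its exclusion is debatable. Whether such holds count as missed is for the trial team to decide, and SAP 5.2 does not say. Neither answer removes the dependence on timing, because early and late gaps are still scored differently.

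A reader might go further and infer that the per-protocol set will contain under-dosed participants at all sites, or that the per-protocol estimate is biased by a known amount. The documents support neither inference. Net resupply is not established at any site, and no frequency of missed or held doses is given.

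**Conclusion.** The point holds in conditional form. Pills dispensed is the wrong denominator for a set that represents treatment as planned. Where resupply is net and issues fall at Baseline and Week 4, the rule depends on when tablets were missed, and steady intake passes from 66.7% of planned rather than 80%. These figures assume nominal visit dates and full return of leftovers. Where a full supply is reissued, nothing is wrong.

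The reach is limited. A reader might infer that the trial's main result is at risk, but the single formal test (SAP 7.7) is analysed by intention to treat (SAP 5.1) and does not use this rule. Both injections are still required for per-protocol entry. Serum buprenorphine at Week 8 (SAP 8.3) gives an outside check on exposure, though it is not part of the definition. The effect on any per-protocol estimate is unknown. This is a cheap improvement of minor severity.

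**What to change.** In SAP 5.2, replace the pills-dispensed criterion with: tablets taken divided by scheduled dosing days from the first tablet to the participant's actual Week 8 visit, at least 80%. Nominally that is 45 of 56 tablets. State that tablets issued at Week 8 do not enter; if that issue of 28 were counted, a fully adherent participant would score 56/84 = 66.7% and fail. Add one sentence saying whether holds or reductions permitted by Protocol 7.3.4 count as missed doses. Make the change before database lock and unmasking.

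The cost is a short edit to one SAP section. No new data are needed, because missed and taken tablets are already recorded. The per-protocol set may become somewhat smaller. If permitted holds count as missed, removals for side effects may be more frequent on active drug, which adds selection to a comparison no longer protected by randomisation. The set should therefore be read alongside the intention-to-treat result.
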